12.5.3. Definition of Cardiovascular Events

| |
|--|
| 
Cardiovascular Events (CV) Definition:
 |
| 
Investigators will be required to fill out the specific CV event page of the CRF for the following AEs and SAEs:
 
 Myocardial infarction/unstable angina Congestive heart failure Arrhythmias Valvulopathy Pulmonary hypertension |

- Cerebrovascular events/stroke and transient ischemic attack
- Peripheral arterial thromboembolism
- Deep venous thrombosis/pulmonary embolism
- Revascularization

12.5.4. Recording of AEs and SAEs

AEs and SAE Recording:

- When an AE/SAE occurs, it is the responsibility of the investigator to review all documentation (e.g., hospital progress notes, laboratory, and diagnostics reports) relative to the event.
- The investigator will then record all relevant information regarding an AE/SAE in the CRF
- It is **not** acceptable for the investigator to send photocopies of the subject's medical records to GSK in lieu of completion of the GSK, AE/SAE CRF page.
- There may be instances when copies of medical records for certain cases are requested by GSK. In this instance, all subject identifiers, with the exception of the subject number, will be blinded on the copies of the medical records prior to submission of to GSK.
- The investigator will attempt to establish a diagnosis of the event based on signs, symptoms, and/or other clinical information. In such cases, the diagnosis will be documented as the AE/SAE and not the individual signs/symptoms.

12.5.5. Evaluating AEs and SAEs

Assessment of Intensity

The investigator will make an assessment of intensity for each AE and SAE reported during the study and will assign it to one of the following categories:

- Mild: An event that is easily tolerated by the subject, causing minimal discomfort and not interfering with everyday activities.
- Moderate: An event that is sufficiently discomforting to interfere with normal everyday activities
- Severe: An event that prevents normal everyday activities. - an AE that is assessed as severe will not be confused with an SAE. Severity is a category utilized for rating the intensity of an event; and both AEs and SAEs can be assessed as severe.
- An event is defined as 'serious' when it meets at least one of the pre-defined outcomes as described in the definition of an SAE.

Assessment of Causality

- The investigator is obligated to assess the relationship between study treatment and the occurrence of each AE/SAE.
- A "reasonable possibility" is meant to convey that there are facts/evidence or arguments to suggest a causal relationship, rather than a relationship cannot be ruled out.
- The investigator will use clinical judgment to determine the relationship.
- Alternative causes, such as natural history of the underlying diseases, concomitant therapy, other risk factors, and the temporal relationship of the event to the study treatment will be considered and investigated.
- The investigator will also consult the Investigator Brochure (IB) and/or Product Information, for marketed products, in the determination of his/her assessment.
- For each AE/SAE the investigator **must** document in the medical notes that he/she has reviewed the AE/SAE and has provided an assessment of causality.
- There may be situations when an SAE has occurred and the investigator has minimal information to include in the initial report to GSK. However, **it is very important that the investigator always make an assessment of causality for every event prior to the initial transmission of the SAE data to GSK.**
- The investigator may change his/her opinion of causality in light of follow-up information, amending the SAE data collection tool accordingly.
- The causality assessment is one of the criteria used when determining regulatory reporting requirements.

Follow-up of AEs and SAEs

- The investigator is obligated to perform or arrange for the conduct of supplemental measurements and/or evaluations as may be indicated or as requested by GSK to elucidate as fully as possible the nature and/or causality of the AE or SAE.
- The investigator is obligated to assist. This may include additional laboratory tests or investigations, histopathological examinations or consultation with other health care professionals.
- If a subject dies during participation in the study or during a recognized follow-up period, the investigator will provide GSK with a copy of any post-mortem findings, including histopathology, if available.
- New or updated information will be recorded in the originally completed CRF.
- The investigator will submit any updated SAE data to GSK within the designated reporting time frames.

[figure not shown]
12.5.6. Reporting of SAEs to GSK

SAE reporting to GSK via electronic data collection tool

- Primary mechanism for reporting SAEs to GSK will be the electronic data collection tool
- If the electronic system is unavailable for greater than 24 hours, the site will use the paper SAE data collection tool and fax it to the Medical Monitor
- Site will enter the serious adverse event data into the electronic system as soon as it becomes available.
- The investigator will be required to confirm review of the SAE causality by ticking the 'reviewed' box at the bottom of the eCRF page within 72 hours of submission of the SAE.
- After the study is completed at a given site, the electronic data collection tool (e.g., InForm system) will be taken off-line to prevent the entry of new data or changes to existing data
- If a site receives a report of a new SAE from a study subject or receives updated data on a previously reported SAE after the electronic data collection tool has been taken off-line, the site can report this information on a paper SAE form or to the Medical Monitor by telephone.
- Contacts for SAE receipt can be found at the beginning of this protocol on the Sponsor/Medical Monitor Contact Information page.

12.6. Appendix 6: ECOG Performance Status¹

CCI - This section contained Clinical Outcome Assessment data collection questionnaires or indices, which are protected by third party copyright laws and therefore have been excluded.

Reference:

12.7. Appendix 7: Modified List of Highly Effective Methods for Avoiding Pregnancy in FRP and Collection of Pregnancy Information

This appendix is **optional** and should **ONLY** be included if study treatment is supplied and information on pregnancies is to be collected for female subjects or for female partners of male study subjects. Female subjects with non-reproductive potential are defined as below:

Pre-menopausal females with one of the following:

- Documented tubal ligation
- Documented hysteroscopic tubal occlusion procedure with follow-up confirmation of bilateral tubal occlusion
- Hysterectomy
- Documented Bilateral Oophorectomy

Postmenopausal defined as 12 months of spontaneous amenorrhea [in questionable cases a blood sample with simultaneous follicle stimulating hormone (FSH) and estradiol levels consistent with menopause (refer to laboratory reference ranges for confirmatory levels)]. Females on hormone replacement therapy (HRT) and whose menopausal status is in doubt will be required to use one of the highly effective contraception methods if they wish to continue their HRT during the study. Otherwise, they must discontinue HRT to allow confirmation of post-menopausal status prior to study enrolment.

12.7.1. Modified List of Highly Effective Methods for Avoiding Pregnancy in Females of Reproductive Potential (FRP)

The list does not apply to FRP with same sex partners or for subjects who are and will continue to be abstinent from penile-vaginal intercourse on a long term and persistent basis, when this is their preferred and usual lifestyle. Periodic abstinence (e.g. calendar, ovulation, symptothermal, post-ovulation methods) and withdrawal are not acceptable methods of contraception.

1. Contraceptive subdermal implant
2. Intrauterine device or intrauterine system
3. Combined estrogen and progestogen oral contraceptive [[Hatcher](#), 2011])
4. Injectable progestogen [[Hatcher](#), 2011]
5. Contraceptive vaginal ring [[Hatcher](#), 2011]
6. Percutaneous contraceptive patches [[Hatcher](#), 2011]
7. Male partner sterilization with documentation of azoospermia prior to the female subject's entry into the study, and this male is the sole partner for that subject [[Hatcher](#), 2011]. The documentation on male sterility can come from the site

personnel's: review of subject's medical records, medical examination and/or semen analysis, or medical history interview provided by her or her partner.

These allowed methods of contraception are only effective when used consistently, correctly and in accordance with the product label. The investigator is responsible for ensuring that subjects understand how to properly use these methods of contraception.

Contraceptive requirements for male subjects with female partners of reproductive potential.

Male subjects with female partners of child bearing potential must comply with the following contraception requirements from the time of first dose of study medication until [at least five half-lives of study medication OR for a cycle of spermatogenesis following five terminal half-lives] after the last dose of study medication.

1. Vasectomy with documentation of azoospermia. The documentation on male sterility can come from the site personnel's: review of subject's medical records, medical examination and/or semen analysis, or medical history interview.
2. Male condom plus partner use of one of the contraceptive options below that meets the SOP effectiveness criteria including a <1% rate of failure per year, as stated in the product label:
 - Contraceptive subdermal implant
 - Intrauterine device or intrauterine system
 - Combined estrogen and progestogen oral contraceptive [[Hatcher](#), 2011]
 - Injectable progestogen [[Hatcher](#), 2011]
 - Contraceptive vaginal ring [[Hatcher](#), 2011]
 - Percutaneous contraceptive patches [[Hatcher](#), 2011]

These allowed methods of contraception are only effective when used consistently, correctly and in accordance with the product label. The investigator is responsible for ensuring that subjects understand how to properly use these methods of contraception.

12.7.2. Collection of Pregnancy Information

- Investigator will collect pregnancy information on any female subject, who becomes pregnant while participating in this study
- Information will be recorded on the appropriate form and submitted to GSK within 2 weeks of learning of a subject's pregnancy.
- Subject will be followed to determine the outcome of the pregnancy. The investigator will collect follow up information on mother and infant, which will be forwarded to GSK. Generally, follow-up will not be required for longer than 6 to 8 weeks beyond the estimated delivery date.
- Any termination of pregnancy will be reported, regardless of fetal status (presence or absence of anomalies) or indication for procedure.

- While pregnancy itself is not considered to be an AE or SAE, any pregnancy complication or elective termination of a pregnancy will be reported as an AE or SAE.
- A spontaneous abortion is always considered to be an SAE and will be reported as such.
- Any SAE occurring as a result of a post-study pregnancy which is considered reasonably related to the study treatment by the investigator will be reported to GSK as described in [Appendix 5](#). While the investigator is not obligated to actively seek this information in former study participants, he or she may learn of an SAE through spontaneous reporting.

Any female subject who becomes pregnant while participating

- will be withdrawn from the study
- Investigator will attempt to collect pregnancy information on any female partner of a male study subject who becomes pregnant while participating in this study.
- After obtaining the necessary signed informed consent from the female partner directly, the investigator will record pregnancy information on the appropriate form and submit it to GSK within 2 weeks of learning of the partner's pregnancy
- Partner will also be followed to determine the outcome of the pregnancy. Information on the status of the mother and child will be forwarded to GSK.
- Generally, follow-up will be no longer than 6 to 8 weeks following the estimated delivery date. Any termination of the pregnancy will be reported regardless of fetal status (presence or absence of anomalies) or indication for procedure.

12.8. Appendix 8: Montreal Cognitive Assessment

CCI - This section contained Clinical Outcome Assessment data collection questionnaires or indices, which are protected by third party copyright laws and therefore have been excluded.

12.9. Appendix 9: Country Specific Requirements

No country-specific requirements exist.

12.10. Appendix 10: IWG CRITERIA FOR RESPONSE

| Category | Response Criteria |
|------------------------------|--|
| Complete Remission | Bone marrow: $\leq 5\%$ myeloblasts with normal maturation of all cell linesa Persistent dysplasia will be noteda,b Peripheral blood (Response must be maintained for at least 4 weeks) Hgb ≥ 11 g/dL Platelets ≥ 100 Gi/L Neutrophils ≥ 1.0 Gi/Lb Blasts 0% |
| Partial Remission | All CR criteria if abnormal before treatment except: Bone marrow blasts decreased by $\geq 50\%$ over pre-treatment but still $> 5\%$ Cellularity and morphology not relevant |
| Marrow CR^b | Bone marrow: $\leq 5\%$ myeloblasts and decrease by $\geq 50\%$ over pre-treatment ^b Peripheral blood: if HI responses, they will be noted in addition to marrow CR ^b |
| HI | Erythroid (HI-E): hgb increase of > 1.5 g/dL decrease of $>$ RBC transfusions/8weeks versus pretreatment requirement in previous 8 weeks; only RBC transfusions given for a pretreatment Hgb of < 9.0 g/dL count Platelet (HI-P): increase of $> 30,000$ /mL (starting with $> 20,000$ /mL) increase from $< 20,000$ /mL to $> 20,000$ /mL by $> 100\%$ Neutrophil (HI-N): increase of $> 100\%$ and > 500 /uL |
| Stable Disease | Failure to achieve at least PR, but no evidence of progression > 8 wks |
| Disease Progression | For subjects with: 
 • Less than 5% BM blasts: $\geq 50\%$ increase in blasts to $> 5\%$ blasts • 5%-<10% BM blasts: $\geq 50\%$ increase to $> 10\%$ blasts • 10%-<20% BM blasts: $\geq 50\%$ increase to $> 20\%$ blasts • 20%-30% BM blasts: $\geq 50\%$ increase to $> 30\%$ blasts Any of the following: 
 • At least 50% decrement from maximum remission/response in granulocytes or platelets • Reduction in Hgb by ≥ 2 g/dL • Transfusion dependence |
| Non-evaluable | Subject does not meet any of the above criteria |

BM = bone marrow ; CR = complete remission; Hgb = hemoglobin;; PR = partial remission

a. Dysplastic changes should consider the normal range of dysplastic changes (modification).

b. Modification to IWG response criteria [[Cheson, 2006](#)].

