2.1.2. Rationale for subject population

Myelodysplastic syndromes (MDS) are clonal disorders of the bone marrow characterized by ineffective hematopoiesis with peripheral blood-cytopenia and a propensity to transform to acute myeloid leukemia (AML). MDS may evolve into AML in up to 45% of patients [Greenberg, 1997]. Differentiation of hematopoietic stem cells is impaired in MDS. Clonal expansion of the abnormal stem cells results in the production of cells which have lost the ability to differentiate into normal blood cells [Fenaux, 2014]. In MDS patients, myeloblasts often constitute more than 5% of the cells in the bone marrow. The number of myeloblasts is one of the principal determinants of

disease severity, where the percentage of blasts of >20% constitutes a transformation to AML. MDS occurs in 3-4 individuals per 100,000 in the US population. Incidence rates increase with age. Individuals age 60 and above have a higher prevalence rate of 7-35 per 100,000 [Rollinson, 2008]. The median age at diagnosis of MDS is 73 years [Mufti, 2012].

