5.1. Inclusion Criteria

A subject will be eligible for inclusion in this study only if all of the following criteria apply:

| AGE |
|--|
| 1. ≥ 18 years of age and provided signed written informed consent |

| TYPE OF SUBJECT AND DIAGNOSIS INCLUDING DISEASE SEVERITY |
|---|
| 
2. Subjects must have IPSS-R high or very high risk myelodysplastic syndromes (MDS) by WHO classification
 
3. Subjects must have failed hypomethylating treatment where “failure” is defined as:
 
 a) Progression (according to 2006 IWG criteria) at any time after initiation of the hypomethylating treatment OR b) Failure to achieve complete or partial response or hematological improvement (HI) (according to 2006 IWG) after at least 4 cycles treatment OR c) Relapse after initial complete or partial response or HI (according to 2006 IWG criteria). 
4. Subjects are not a candidate, or have failed allogeneic stem cell transplantation. Subjects who underwent allo-transplant in the past are eligible under following conditions:
 
 a) transplant was ≥ 2 year prior to enrolment, and b) no evidence of active GVHD 
5. Eastern Cooperative Oncology Group (ECOG) performance status of 0-1.
 
6. Subjects must have a life expectancy of at least 12 weeks, in the opinion of the investigator.
 
7. Able to swallow and retain orally administered medication and does not have any clinically significant gastrointestinal abnormalities that may alter absorption such as malabsorption syndrome or major resection of the stomach or bowels.
 
8. All prior treatment-related toxicities must be National Cancer Institute- Common Toxicity Criteria for Adverse Events (NCI-CTCAE), version 4.0 \leq Grade 1 at the time of enrollment (except for alopecia).
 |

LABORATORY

9. Adequate baseline organ function defined by:

| System | Laboratory Values |
|--|--|
| Coagulation | |
| INR and aPTT | ≤1.3 X ULN |
| Hematologic | |
| PLT | ≥10,000 (transfusions permitted to bring platelet count to >10,000) |
| Hepatic | |
| Total bilirubin | ≤ 1.5 X ULN ^a |
| ALT | ≤2.5 × ULN |
| Renal | |
| Creatinine | ≤1.5 X ULN |
| OR | |
| Calculated creatinine clearance by Chronic Kidney Disease Epidemiology Collaboration (CKD-EPI) equation (Appendix 3) or measured from 24hr urine | ≥ 50 mL/min |
| Cardiac | |
| Ejection fraction | ≥ LLN by Echocardiogram (ECHO) or MUGA |

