5.2. Exclusion Criteria

A subject will not be eligible for inclusion in this study if any of the following criteria apply:

DIAGNOSTIC ASSESSMENTS AND OTHER CRITERIA

1. AML according to WHO criteria (i.e. bone marrow blasts >20%)
2. Active hepatitis B or hepatitis C treatment
3. Baseline (pre-dose Day 1) Montreal Cognitive Assessment (MOCA) score of 22 or lower

CONCURRENT CONDITIONS/MEDICAL HISTORY

4. History of or concurrent malignancy of solid tumours, except for below:
Exception: Subjects who have been disease-free for 2 years, or subjects with a history of completely resected non-melanoma skin cancer or successfully treated in situ carcinoma are eligible. Consult GSK Medical Monitor if unsure whether second malignancies meet requirements specified above
5. Prior treatment with temozolomide, dacarbazine or procarbazine
6. Prior treatment with poly ADP ribose polymerase (PARP) inhibitors (e.g., olaparib, ABT-888)
7. Currently receiving other anti-cancer therapy (chemotherapy, radiation therapy, immuno-therapy, biologic therapy, hormonal therapy, surgery, and/or tumour embolization)
8. Received major surgery, radiotherapy, or immunotherapy within 4 weeks of GSK2879552 administration
9. Evidence of severe or uncontrolled systemic diseases (e.g., severe/chronic infection, unstable or uncompensated respiratory, renal, or cardiac disease). Any serious and/or unstable pre-existing medical (aside from malignancy exception above), psychiatric disorder, or other conditions that could interfere with subject's safety, obtaining informed consent or compliance to the study procedures, in the opinion of the Investigator
10. Current active liver or biliary disease (with the exception of Gilbert's syndrome or asymptomatic gallstones or otherwise stable chronic liver disease per investigator's assessment)
11. Patients with any major bleeding current or within the past 4 weeks. (e.g. recent GI hemorrhage or neurosurgery).
12. Administration of an investigational drug within 14 days or 5 half-lives, whichever is shorter, preceding the first dose of study treatment(s) in this study.
13. Cardiac abnormalities as evidenced by any of the following:
 - Clinically significant uncontrolled arrhythmias or uncontrolled hypertension.
 - History or evidence of current \geq Class II congestive heart failure as defined by New York Heart Association (NYHA)
 - History of acute coronary syndromes (including unstable angina and myocardial

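### Marrow CR has no baseline blast floor and no duration rule, so a subject entering at 5% blasts or less can become an ORR responder on counting variation alone

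*Protocol*

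**What the plan says.** The Marrow CR row of Appendix 10 has two conditions: at most 5% "myeloblasts and decrease by $\geq 50\%$ over pre-treatment". Blood-count improvement is only noted alongside it and is not required. The 4-week rule, "Response must be maintained for at least 4 weeks", stands in the Complete Remission row, not in this one. The Partial Remission row is tied to "All CR criteria if abnormal before treatment except" and needs blasts that remain above 5%.

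Eligibility limits blasts from above only. Section 5.1 says "Subjects must have IPSS-R high or very high risk myelodysplastic syndromes (MDS) by WHO classification", and Section 5.2 excludes "AML according to WHO criteria (i.e. bone marrow blasts >20" percent. Section 2.1.2 says that in MDS "myeloblasts often constitute more than 5% of the cells in the bone marrow", so often but not always. The progression row of Appendix 10 has a stratum "Less than 5% BM blasts".

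Section 3.2 counts mCR in both CBR and ORR and names both as Part 2 primary endpoints. Section 9.4.1 counts mCR as a response for duration of response.

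**The concern.** A subject at or below 5% blasts at entry already meets the first condition. The second is a relative fall, and on a small percentage a halving is a difference of a few cells. Such a subject can become a marrow CR with no true change in the marrow, no change in blood counts and no repeat sample.

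At stake are ORR, which Section 9.4.1 reports by arm with an exact confidence interval and as a difference between arms, and duration of response, which would start from an event that did not occur.

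**Working it through.** **Inputs from the protocol.** The marrow CR rule (Appendix 10); 28 subjects per arm, alpha 0.099 and power 81% (Section 9.2.1); success at 12 or more of 28 and the Table 5 futility limits (Section 9.1.2).

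**Assumptions, not in the protocol.** Number of marrow cells counted (200 or 500); true blasts of 2%, 3% or 4% with no true change; one follow-up marrow; 5% to 20% of entrants with observed blasts of 5% or less.

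**1. The plan's own figures.** An exact binomial recursion through the Table 5 limits gives alpha 0.0991 at a rate of 0.30 and power 0.8174 at 0.50, so the stated figures reproduce. They describe CBR. ORR has no null value, threshold or stopping limit.

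**2. The rule applied to one subject.** Baseline 4%, later 2%: 2% is at most 5%, and (4 − 2)/4 = 50%. Both conditions are met.

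**3. Chance of a false marrow CR.** Let X1 and X2 be the baseline and follow-up blast counts, independent Binomial(n, f). The first condition holds automatically here, so the probability is P(X2 ≤ X1/2 | 0 < X1 ≤ 0.05n).

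| True blasts f | n = 200 cells | n = 500 cells |
|---|---|---|
| 2% | 22.1% | 8.2% |
| 3% | 13.7% | 3.8% |
| 4% | 6.9% | 1.0% |

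For the exact example (observed baseline 4%, true value 4%, follow-up at or below 2%) the chance is 9.5% with 200 cells and 1.0% with 500.

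**4. False responders per arm.** Expected number = 28 × share of low-blast entrants × probability.

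- 200 cells: 28 × 0.05 × 0.069 = 0.10, up to 28 × 0.20 × 0.221 = 1.24.
- 500 cells: 28 × 0.05 × 0.010 = 0.01, up to 28 × 0.20 × 0.082 = 0.46.

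Each adds 1/28 = 3.6 points to ORR if the subject is not already a responder by another route. In points of ORR the ranges are 0.05 × 6.9 = 0.3 to 0.20 × 22.1 = 4.4 with 200 cells, and 0.05 × 1.0 = 0.05 to 0.20 × 8.2 = 1.6 with 500.

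**5. Effect of a floor at more than 5%.** Over all observed baselines with 200 cells and no true change, the chance of a false marrow CR falls from 22%, 15% and 11% to 0.2%, 2% and 5% at true blasts of 2%, 3% and 4%. Noise remains above the floor: given an observed baseline over 5%, the chance is 15% at true 5% and 8% at true 6% with 200 cells, and 2% and 0.6% with 500.

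**The case against.** The strongest reply is that the trial's decision does not rest on ORR. Hypotheses, futility limits and the 12-of-28 rule all concern CBR, which includes stable disease. A subject with no true change counts as stable once free of progression for more than 8 weeks, with or without marrow CR. The label could matter to CBR only for a subject who lacks that stability, and the CBR wording in Section 9.1.2 does not list mCR at all. This stands. A reader might infer that the gap inflates the type I error of the Part 2 test; the documents do not support that.

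A reader might also infer from the stratum "Less than 5% BM blasts: $\geq 50\%$ increase in blasts to $> 5\%$ blasts" that low-blast entrants are expected. That is too strong: the same list has a 20% to 30% stratum although blasts above 20% are excluded at entry. The list shows only that the table covers such subjects. They are admissible, and their share is unknown. High-risk disease may make them a minority.

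It is tempting to add that the risk grows with each further marrow. It would, but on-study marrows are taken only when clinically indicated or to confirm a response (Sections 7.1 and 7.4), so serial sampling cannot be presumed. Nor does the mention of confirming a response supply a repeat-marrow rule for mCR.

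Finally, the endpoint is declared to follow the 2006 IWG criteria, so a floor is a trial-specific departure. This is a fair cost, but Appendix 10 already marks its Marrow CR row as a modification, and its wording is what defines the endpoint here.

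**Conclusion.** The gap is real and confined to ORR and duration of response. As written, a reading of 4% followed by 2% is a response, and no other section supplies a floor or a persistence rule.

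On the assumptions stated, the upward bias in ORR lies between near zero and about 4 points per arm. The upper end needs 200-cell counts, a 20% share of low-blast entrants and true blasts near 2%. With 500 cells it stays under 2 points. The denominator of 28 holds for Part 2 alone; Section 9.4.1 allows Part 1 subjects on the same dose to be pooled. The CBR test and its operating characteristics need no change. The correction is worth making because ORR is a named primary endpoint and one clause removes most of the false responses among subjects with truly low blast counts.

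**What to change.** In the Marrow CR row of Appendix 10, add that the category applies only to subjects with more than 5% marrow blasts at baseline. State that subjects at 5% or less can still respond through CR, HI or cytogenetic response, or count as stable disease, so that the ORR definition in Section 3.2 stays intact for them.

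The costs are one clause, a declared departure from the adopted IWG table, and a possibly slightly lower ORR. The sample size and Table 5 are unchanged. The clause does not remove counting error for baselines just above 5%.

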5.5.3. Dose Adjustment for Hematologic Toxicity

The dose of azacitidine and/or GSK2879552 may be adjusted based on neutrophil, platelet, WBC and bone marrow biopsy cellularity at baseline and nadir according to the guidelines below:

No dose adjustments are needed for anemia.

For patients with baseline (start of treatment) $WBC \geq 3.0 \times 10^9/L$, $ANC \geq 1.5 \times 10^9/L$, and platelets $\geq 75.0 \times 10^9/L$, adjust the dose as follows, based on nadir counts for any given cycle:

| Nadir Counts | | % Dose of Azacitidine/GSK2879552 to be administered |
|---------------------------|---------------------------------|---|
| Course | | - |
| ANC (x10 ⁹ /L) | Platelets (x10 ⁹ /L) | |
| <0.5 | <25.0 | 50%/50-67% |
| 0.5 –1.5 | 25.0-50.0 | 67%/67-100% |
| >1.5 | >50.0 | 100%/100% |

For patients whose baseline counts are $WBC < 3.0 \times 10^9/L$, $ANC < 1.5 \times 10^9/L$, or platelets $< 75.0 \times 10^9/L$, dose adjustments should be based on nadir counts and bone marrow biopsy cellularity at the time of the nadir as noted below, unless there is clear improvement in differentiation (percentage of mature granulocytes is higher and ANC is higher than at onset of that course) at the time of the next cycle, in which case the dose of the current treatment should be continued.

| WBC or Platelet Nadir % decrease in counts from baseline | Bone Marrow Biopsy Cellularity at Time of Nadir (%) | | |
|--|---|------------|------------|
| | 30-60 | 15-30 | <15 |
| % Dose of Azacitidine/GSK2879552 to be administered - | | | |
| 50 - 75 | 100%/100% | 50%/33-67% | 33%/25-50% |
| >75 | 75%/50-100% | 50/33-67% | 33%/25-50% |

If a nadir as defined in the table above has occurred, the next course of treatment should be given 28 days after the start of the preceding course, provided that both the WBC and the platelet counts are >25% above the nadir and rising. If a >25% increase above the nadir is not seen by day 28, counts should be reassessed every 7 days. If a 25% increase is not seen by day 42, then the patient should be treated with 50% of the scheduled dose.

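### The main haematologic improvement (HI) branches in Appendix 10 have no upper baseline limit, so a lineage already at the table's CR level can score HI and inflate ORR

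*Protocol*

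**What the plan says.** Protocol Section 7.4 sends the reader to Appendix 10 (Section 12.10) for the response criteria. The HI row there has these branches:

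- **Erythroid:** "hgb increase of > 1.5 g/dL", with no baseline haemoglobin limit. The alternative is a fall in RBC transfusion need, where "only RBC transfusions given for a pretreatment Hgb of" less than 9.0 g/dL count.
- **Platelet:** a rise above 30,000, "starting with" more than 20,000. That is a floor without a ceiling. The alternative is a rise from below 20,000 to above 20,000 by more than 100%.
- **Neutrophil:** a rise above 100% and above 500/uL, with no baseline limit.

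Only the two alternative branches imply a low baseline, and they do not restrict the main ones. No duration is written for HI.

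Other rows of the same table are tighter. CR needs Hgb of at least 11 g/dL, platelets of at least 100 and neutrophils of at least 1.0 x10^9/L, with the condition "Response must be maintained for at least 4 weeks". PR reads "All CR criteria if abnormal before treatment except" for the marrow blast item.

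HI counts in both ORR and CBR, the Part 2 primary endpoints (Section 3.2). Section 9.4.1 counts a response at any time and starts duration of response at the first response, HI included.

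**The concern.** HI should record recovery of a cell line that the disease had suppressed. As written, platelets going from 150 to 182 x10^9/L, neutrophils from 2.0 to 4.1 x10^9/L, or Hgb from 11.5 to 13.1 g/dL each meet an HI branch, although that lineage already satisfied the CR limit before treatment.

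Such subjects can be enrolled. Section 5.1 sets only a platelet floor of 10,000 and requires no cytopenia in any lineage. Section 5.5.3 has a dose table opening "For patients with baseline (start of treatment" that covers neutrophils of at least 1.5 x10^9/L, above the CR limit of 1.0.

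Three results are exposed:

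- **ORR**, where one HI makes a responder.
- **Duration of response**, which then includes subjects whose response was a fluctuation.
- **CBR**, to a smaller extent: subjects who score a chance HI and progress before stable disease is reached, and futility looks taken early. Section 9.1.2 makes a subject evaluable after one post-treatment assessment; Section 9.3.2.1 puts assessments every 4 weeks; stable disease needs more than 8 weeks. At such a look a chance HI can count where stable disease cannot yet.

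Rebound is a second route besides chance. Section 2.2.3.2 reports platelet and neutrophil rebound in animals after dosing stopped, and Section 5.5.1.1 allows granulocyte growth factors for febrile neutropenia.

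**Working it through.** **1. The plan's own figures.** An exact binomial recursion through the Table 5 futility bounds (looks at 10, 12, ..., 28; success at 12 or more of 28) gives:

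| True CBR | Probability of success | Protocol, Section 9.2.1 |
|---|---|---|
| 0.30 | 0.0991 | 0.099 |
| 0.50 | 0.8174 | 81% |

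Early termination at 0.50 is 1 - 0.8174 = 0.183, as stated.

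**2. Chance HI in a preserved lineage.** Baseline and later counts are drawn from a lognormal distribution with the same mean. Only baselines at or above the Appendix 10 CR limit are kept, and each HI branch is applied literally, taking 30,000 platelets as 30 x10^9/L. The within-subject CVs are assumptions; the documents give none.

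| Lineage, mean, assumed CV | 1 visit | 2 visits | 3 visits |
|---|---|---|---|
| Hgb 11.5 g/dL, 7% | 3% | 6% | 9% |
| Neutrophils 2.0 x10^9/L, 30% | 4% | 7% | 10% |
| Platelets 150 x10^9/L, 10% | 8% | 14% | 18% |
| Platelets 150 x10^9/L, 15% | 17% | 28% | 36% |
| Platelets 150, 15%, mean falls 20% on treatment | 1.6% | 3.0% | 4.3% |
| Platelets 150, 10%, mean falls 20% on treatment | 0.1% | 0.2% | 0.2% |

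The 20% fall is also an assumption. Its direction follows from Section 2.2.4: a median platelet nadir of 29 x10^9/L in five lung cancer subjects at 2 mg daily.

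**3. Effect on ORR.** The increase is at most share x rate, where share is the proportion of subjects with one preserved lineage (assumed 20-50%; not in the documents). For Hgb or neutrophils at one visit: 0.2 x 0.03 = 0.6 points to 0.5 x 0.04 = 2.0 points. Over three visits: 0.2 x 0.09 = 1.8 points to 0.5 x 0.10 = 5.0 points.

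**4. Effect on CBR.** Only subjects without true benefit (70% under the null) can be miscounted, and only if they progress before stable disease is reached, which leaves about one or two visits. With the one-visit Hgb and neutrophil rates, the rise in null CBR is at most 0.7 x share x rate:

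- low end: 0.7 x 0.2 x 0.03 = 0.0042
- high end: 0.7 x 0.5 x 0.04 = 0.014

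The recursion then gives a type I error of 0.108 at CBR 0.3042 and 0.131 at 0.314, against 0.099. This takes every subject without true benefit as progressing early, which overstates the effect for the assumed shares and rates.

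**The case against.** **The standard may already supply the limit.** The protocol ties response to the 2006 IWG criteria in several places, and the HI row as read here has lost content: the number of RBC transfusions is missing and the platelet unit reads per mL. A baseline condition may have been intended. This stands as a reason for caution. It does not remove the point: no section supplies a limit, and footnote b of Appendix 10 declares modifications to the criteria, so a site cannot tell omission from intent.

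**Counts are likely to fall.** The drug lowers platelets, and azacitidine adds overlapping haematological toxicity (Section 4.10.2). This stands and removes most of the platelet effect. It does not exclude rebound after an interruption.

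**ORR drives no per-arm decision.** The hypothesis, futility bounds and 12-of-28 rule all use CBR. That is correct, but ORR is named as a Part 2 primary endpoint and will be reported with a confidence interval.

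**One value may not suffice.** Section 9.1.2 speaks once of a confirmed response rate, and Section 7.4 asks for marrow to confirm response. Neither states a confirmation rule for a rise in counts.

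**Stronger readings a reader might infer.** One is that type I error rises to about 0.24. That needs a null CBR of 0.35, a 5-point shift which nothing in the documents yields. Another is that ORR rises by 4-10 points. That needs a 20% chance-HI rate, which the Hgb and neutrophil figures above do not reach and platelets reach only when their mean stays level. A third is that Section 5.5.3 shows preserved lineages to be common. It gives no prevalence, does not mention haemoglobin, and its platelet limit (75) lies below the CR limit.

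**Conclusion.** The point holds on the text. The three main HI branches have no upper baseline limit, the PR row beside them has one, and eligibility admits subjects with preserved lineages. Followed literally, the rule credits improvement in a lineage that was not abnormal.

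The harm falls mainly on ORR and duration of response. CBR is touched only through chance HI before early progression and through early futility looks; the illustration puts type I error at about 0.11-0.13 instead of 0.099. All sizes depend on within-subject variability, the share of subjects with a preserved lineage, and the course of mean counts on treatment, none of which the documents fix. They show the direction and a plausible range and are not forecasts. The text should be corrected; the finding does not invalidate the Part 2 design.

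**What to change.** Add one sentence to the HI row of Appendix 10: HI is assessed only in lineages abnormal before treatment, meaning Hgb below 11 g/dL, platelets below 100 x10^9/L or neutrophils below 1.0 x10^9/L. These are the complements of the CR limits already in the table, and the sentence does for HI what the PR row does for PR. Before adopting them, reconcile the limits with the 2006 IWG criteria that the protocol cites, so that the sentence does not create an unintended departure.

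The cost is one appendix sentence. Baseline counts are already collected at screening and Day 1. Reported HI and ORR, and possibly CBR, may be slightly lower.
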